# 5.3. Analysis Populations

#### **5.3.1.** All-Screened Population

The all-screened population includes all participants who signed the informed consent form. The all-screened population will be used for the summary of analysis populations.

#### 5.3.2. Full Analysis Set

The FAS includes all participants enrolled in the study who received at least 1 dose of INCB050465.

The FAS will be used for the summary of demographics, baseline characteristics, participant disposition, and analyses of all efficacy data.

#### **5.3.3.** Safety Population

The safety population includes all participants enrolled in the study who received at least 1 dose of INCB050465.

All safety analyses will be conducted using the safety population.

# 6. BASELINE, EXPOSURE, AND DISPOSITION VARIABLES AND ANALYSES

Appendix A provides a list of planned tables, figures, and listings. Sample data displays are included in a separate document.

# 6.1. Baseline and Demographics, Physical Characteristics, and Disease History

#### **6.1.1.** Demographics and Baseline Characteristics

The following demographics will be summarized and listed for the FAS: age, sex, race, ethnicity, weight, height, BMI, and geographic region. Eastern Cooperative Oncology Group performance status at baseline will be summarized and listed for the FAS.

#### 6.1.2. Disease History

Time since diagnosis, initial grade, initial cytogenetics, initial Ann Arbor staging, initial FLIPI risk category, initial presence of B-symptoms, current grade, current cytogenetics, current Ann Arbor staging, current FLIPI risk category, current presence of B-symptoms, bone marrow involvement at baseline (Yes vs No), bulky disease at baseline (longest diameter ≥ 10 cm vs < 10 cm) at baseline by the IRC, and relapsed/refractory status to the most recent prior therapy

will be summarized and listed for all participants in the FAS. Date of tumor marker tests and test results will be listed.

Time since diagnosis will be calculated as follows:

Time since diagnosis (years) = (Day 1 date – date of diagnosis + 1) / 365.25.

#### 6.1.3. Prior Therapy

Number of prior systemic cancer therapy regimens will be summarized for all participants in the FAS. The component drugs of prior systemic therapy regimens will be coded using the WHO Drug Dictionary. Number and percentage of participants with each drug will be summarized by WHO drug class and WHO drug PT. Regimen name, component drugs, start and stop date, route of the medication, best response, reason for discontinuation, and date of relapse/progression will be listed.

Number of participants who received prior radiation will be summarized for the FAS. Anatomical location of the administration, start and stop date, and total dose will be listed.

Number of participants who had prior surgery or surgical procedure for the malignancies under study will be summarized for the FAS. Date and description of the surgery/procedure will be listed.

Number of participants who had prior hematopoietic stem cell transplant will be summarized for the FAS. Date of transplant, type of transplant, source of cells, line of therapy, best response, date of relapse/progression, and regimen and drug used with the transplant will be listed.

#### 6.1.4. Medical History

Medical history will be coded to SOC and PT using MedDRA coding dictionary. For participants in the FAS, medical history will be summarized by SOC and PT and listed.

# **6.2.** Disposition of Participants

The number and percentage of participants who were treated, who were ongoing with study treatment, who discontinued study treatment with a primary reason for discontinuation, who were still in the study, and who withdrew from the study with a primary reason for withdrawal will be summarized for the FAS.

The number of participants enrolled by country and site will also be provided for the FAS.

#### **6.3.** Protocol Deviations

Protocol deviations recorded on the eCRF will be summarized and listed for the FAS.

## 6.4. Exposure

For participants in the safety population, exposure to INCB050465 will be summarized descriptively as the following:

• **Duration of treatment (days)**: Date of last dose – date of first dose + 1.

- **Duration of treatment during the initial QD dosing period (days)**: Date of last dose during initial QD dosing period date of first dose + 1.
- Duration of treatment during the maintenance dosing period (days): Date of last dose date of first dose during the maintenance dosing period + 1. Crossover participants who switched to the selected treatment regimen after the start of the maintenance dosing period will be summarized in a separate group (ie, Crossover).
- Average reported daily dose during the initial QD dosing period (mg/day): Total reported dose taken during initial QD dosing period (mg) / duration of treatment during the initial QD dosing period (days).
- Average reported daily dose during the maintenance dosing period (mg/day): Total reported dose taken during the maintenance dosing period (mg) / duration of treatment during the maintenance dosing period (days). Crossover participants who switched to the selected treatment regimen after the start of the maintenance dosing period will be summarized in a separate group (ie, Crossover).
- **Dose modifications:** Number of participants who had dose reduction and interruption will be summarized. The number of dose reductions and the number of interruptions for each participant will be summarized.

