5.4. Treatment Interruptions and Adjustments

5.4.1. Criteria and Procedures for Dose Interruptions and Reductions of INCB050465

Treatment with INCB050465 may be interrupted for up to 14 days to allow for resolution of toxicity. Subjects may resume treatment if no medical condition or other circumstance exists that, in the opinion of the investigator, would make the subject unsuitable for further participation in the study. The treating investigator should contact the sponsor to discuss the case of any subject whose treatment has been interrupted for more than 14 days before restarting treatment with INCB050465.

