Timepoint	Dose (Group A)	Dose (Group B)
Starting dose	20 mg QD for 8 weeks (Day 1 through Day 56)	20 mg QD for 8 weeks (Day 1 through Day 56)
First dose reduction	10 mg QD	10 mg QD
Second dose reduction	5 mg QD	5 mg QD
Week 9 (Day 57) onward	20 mg once weekly ^a	2.5 mg QD ^b
First dose reduction	10 mg once weekly	1 mg QD ^c
Second dose reduction	5 mg once weekly	NA

^a All subjects will receive 20 mg once weekly at Week 9 (Day 57) regardless of prior dose level, unless a dose modification of a switch to a QW schedule before Week 9 is required for diarrhea/colitis management (see [Table 5](#)).

^b All subjects will receive 2.5 mg QD at Week 9 (Day 57) regardless of prior dose level, unless a dose modification of a switch to a QW schedule is required for diarrhea/colitis management (see [Table 5](#)).

^c Further dose modification due to diarrhea or colitis for subjects on 1 mg QD is permitted (see [Table 5](#)).

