5.5.1. Criteria for Study Treatment Discontinuation

Subjects **must** permanently discontinue study treatment for any 1 of the following:

- The subject has experienced an unacceptable toxicity defined as follows:
 - Occurrence of an AE that is related to study treatment that, in the judgment of the investigator or the sponsor's medical monitor, compromises the subject's ability to continue study-specific procedures or is considered to not be in the subject's best interest.
 - Persistent AE requiring a delay of therapy for more than 2 weeks (14 days) unless a greater delay has been approved by the sponsor.
- The subject is unable to tolerate study treatment.
- The subject has an objective radiographic tumor response of PD/PMD.
- Further participation would be injurious to the subject's health or well-being, in the investigator's medical judgment.
- The subject becomes pregnant.

- Informed consent is withdrawn. Note: Consent withdrawn means that the subject can no longer be followed. Subjects may choose to discontinue study treatment and remain in the study to be followed for disease progression and survival per the schedule of assessments.
- The study is terminated by the sponsor.
- The study is terminated by the local health authority, IRB, or IEC.

A subject **may** be discontinued from study treatment in the following situations:

- If a subject is noncompliant with study procedures or study treatment administration in the investigator's opinion, then the sponsor should be consulted for instruction on handling the subject.

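### SAP 6.4 leaves drug-free days between the last initial-QD dose and the first maintenance dose out of both period durations, so period average doses are overstated for participants with a hold across Day 56/57.

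*SAP*

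**What the plan says.** SAP 6.4 (Exposure) defines three durations.

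- Overall: "Date of last dose – date of first dose + 1".
- Initial QD period: "Date of last dose during initial QD dosing period date of first dose + 1".
- Maintenance period: "Date of last dose date of first dose during the maintenance dosing period + 1".

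The extracted text of the last two has lost a minus sign. I read both as last date minus first date plus 1, like the overall formula.

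The average daily dose for the lead-in is "Total reported dose taken during initial QD dosing period (mg) / duration of treatment during the initial QD dosing period (days"), and the maintenance average is built the same way. SAP 6.4 defines no average dose over the whole treatment period. It summarizes interruptions as the number of participants affected and the number per participant, not as days off drug.

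Protocol Table 4 sets the lead-in as "20 mg QD for 8 weeks (Day 1 through Day 56") in both groups. The change to maintenance goes by calendar. For Group B, "All subjects will receive 2.5 mg QD at Week 9 (Day 57) regardless of prior dose level", with an exception for diarrhea/colitis management; Group A has the parallel footnote.

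On holds, Protocol 5.4.1 says: "Treatment with INCB050465 may be interrupted for up to 14 days to allow for resolution of toxicity". Longer holds can occur. One of the mandatory discontinuation criteria in Protocol 5.5.1 is "Persistent AE requiring a delay of therapy for more than 2 weeks (14 days) unless a greater delay has been approved by the sponsor".

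**The concern.** Each period's denominator runs only between doses actually taken. A hold in the middle of the lead-in has QD doses on both sides, so its days are counted and the average falls. A hold that runs up to or across the change to maintenance has no QD dose after it, so its days drop out of the lead-in. They do not enter maintenance either, because that clock starts at the first maintenance dose.

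This has two consequences. Participants with equal interruptions get different average doses, depending only on where the hold fell. The two period durations also fail to add up to overall duration of treatment. A reader of the lead-in exposure table would see full daily dosing for someone who missed part of the planned 8 weeks.

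**Working it through.** The documents state no average dose and no count of days lost, so there is no figure of theirs to reproduce.

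**Inputs.** Planned lead-in 56 days at 20 mg QD, maintenance from Day 57 (Protocol Table 4). Usual hold limit 14 days (Protocol 5.4.1), longer with sponsor approval (Protocol 5.5.1). Denominators from SAP 6.4.

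**Two participants with the same 14-day hold.** Each takes 42 doses in the lead-in: 42 × 20 = 840 mg.

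- Off drug Days 15-28, last QD dose Day 56: 840 / 56 = 15.0 mg/day.
- Off drug Days 43-56, last QD dose Day 42, maintenance from Day 57: 840 / 42 = 20.0 mg/day.

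In the second case 14 days sit in neither period, yet they are inside the overall duration.

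**General size for the lead-in.** Let L be the study day of the last QD dose. SAP 6.4 gives total dose / L; over the planned lead-in the average is total dose / 56. Total dose cancels, so the overstatement is 56/L − 1 at any dose level.

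| Days lost before Day 57 | L | Overstatement |
|---|---|---|
| 7 | 49 | 56/49 − 1 = 14.3% |
| 14 | 42 | 56/42 − 1 = 33.3% |
| 21 (assumed, needs approval) | 35 | 56/35 − 1 = 60% |
| 28 (assumed, needs approval) | 28 | 56/28 − 1 = 100% |

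A 14-day hold split evenly over the boundary (Days 50-63) has L = 49, so the lead-in is overstated by 14.3%. The other 7 days are missing from maintenance.

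**Maintenance.** If h days of hold fall after Day 56 and the last dose comes M days after Day 56, the maintenance average under daily dosing is overstated by M/(M − h) − 1. With h = 7, this is 84/77 − 1 = 9.1% for M = 84 and 308/301 − 1 = 2.3% for M = 308 (both values of M assumed).

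**Group mean of the lead-in dose.** Suppose a share f has the full 14-day gap on Days 43-56 and everyone else takes 20 mg daily. SAP 6.4 reports 20; the average over 56 days is 20(1 − f) + 15f.

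- f = 10%: 20/19.5 − 1 = 2.6%.
- f = 20%: 20/19.0 − 1 = 5.3%.

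These shares are assumptions.

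**Whether another summary recovers the lost days.** Interruptions are counted, not measured in days. Compliance (SAP 6.5) divides by a prescribed dose that already allows for dose modifications, so a hold ordered by the investigator need not lower it. Overall duration contains the gap but has no average dose attached to it.

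**The case against.** The strongest reply is that SAP 6.4 plans only a descriptive average reported dose. It sets no 56-day benchmark and does not require the period durations to sum to the total. Counting from dose to dose is also the convention for overall duration. Interruptions are visible elsewhere: in the counts in SAP 6.4, the adverse event summaries by period in SAP 9.2.3, Table 3.2.19, and Listings 2.5.2 and 2.7.6. This stands as a limit on importance. It does not explain why the same hold is counted in one position and dropped in another, and none of those outputs corrects either average.

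A reader might also infer more than the documents support.

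- **That 33% is a ceiling.** It is one case: exactly 14 days off, all on Days 43-56, restart on Day 57. Longer approved holds give more; most placements of a 14-day hold give less.
- **That holds near Week 8 are likely.** The 22% rate of Grade 3 or higher neutropenia in Protocol 1.3 covers all of Study 101 treatment (median 114 days) and is not timed to Week 8. Hematology is checked every 2 weeks throughout the first 8 weeks, not only near the end. A hold begun at Week 6 that ends before Day 56 is followed by QD doses and is counted in full. One begun on Day 57 leaves the lead-in average correct.
- **That 56 days is everyone's benchmark.** Participants moved to weekly dosing before Week 9 for diarrhea/colitis have a shorter lead-in by design. For those in Group A, whose weekly period SAP 5.2 treats as maintenance, the gap before the first weekly dose is uncounted too.

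**Conclusion.** The point holds as a defect in the definition. SAP 6.4 gives different averages for equal interruptions and overstates the period average doses of participants whose hold crosses Day 56/57. Relative to the planned 56 days, the lead-in overstatement per affected participant is 56/L − 1.

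The effect on the reported group mean cannot be determined from the documents, because they give no frequency of such holds. A few percent is what the assumed shares of 10% and 20% imply. The effect stops at descriptive exposure: ORR, the futility rule and the other efficacy analyses do not use these averages. It is a minor point, worth correcting because the correction is cheap.

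**What to change.** For participants who start maintenance, end the lead-in at the earlier of (a) the day before the first maintenance dose and (b) the later of Day 56 and the last initial-QD dose. Count maintenance from the next day through the last dose. Each dose then stays in the period in which it was taken, and the two durations sum to overall duration. The hold on Days 43-56 gives 840/56 = 15 mg/day, as it should.

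A plain cap at Day 56 would not do. Table 6 allows ±3 days around the visit, so QD dosing could run to Day 59, and 59 × 20 / 56 = 21.1 mg/day exceeds the daily dose taken. The rule above gives 1180/59 = 20. It also leaves no uncounted days if maintenance starts before Day 57.

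For participants who never start maintenance, keep last dose minus first dose plus 1. In addition, report total days interrupted by period. This captures a hold that ends in discontinuation, which no dose-to-dose denominator can show.

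The cost is a wording change in SAP 6.4, a small programming change, and slightly lower reported average doses.

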#### 5. STATISTICAL METHODOLOGY

## 5.1. General Methodology

Unless otherwise noted, SAS® software (SAS Institute Inc, Cary, NC; v9 or later) will be used for the generation of all tables, graphs, and statistical analyses. Descriptive summaries for continuous variables will include, but not be limited to, the number of observations, mean, standard deviation, median, minimum, and maximum. Descriptive summaries for categorical variables will include the number and percentage of participants in each category.

Interim analyses are planned for this study as defined in Section 10.

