# **5.2.** Treatment Groups

This is a Phase 2, multicenter, open-label study. For the purpose of analysis, the 20 mg once weekly dosing period in Group A and the 2.5 mg QD dosing period in Group B are considered maintenance dosing periods. Data will be presented in summary tables by actual received treatment regimen and combined, with an exception for participants who cross over to the selected treatment regimen after the start of the maintenance dosing period. There will not be any statistical comparison between the treatment groups.

For participants who cross over from the initially assigned treatment regimen to the selected treatment regimen, if the crossover happens on/before the start of the maintenance period, then the participant will be summarized, according to the actual received treatment, in the selected treatment regimen; otherwise, the participant will be summarized in:

- A separate treatment regimen (ie, Crossover) for the safety summaries during the maintenance dosing period (eg. summaries of TEAEs and exposure).
- The initially assigned treatment regimen for all other summaries.

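### SAP 6.4's average daily dose in maintenance runs high by up to 6/D (D = maintenance days) when the last dose was weekly: about 2% at 52 weeks of treatment, more for short exposures

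*SAP*

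**What the plan says.** SAP Section 6.4 gives the average reported daily dose in maintenance as "Total reported dose taken during the maintenance dosing period (mg) / duration of treatment during the maintenance dosing period (days"). The duration in that denominator is "Date of last dose date of first dose during the maintenance dosing period + 1" (a minus sign belongs between the two dates, as in the overall treatment duration defined in the same section).

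SAP Section 5.2 applies this to both regimens: "the 20 mg once weekly dosing period in Group A and the 2.5 mg QD dosing period in Group B are considered maintenance". Data are tabulated by regimen actually received and combined. On crossovers, Section 5.2 says that "if the crossover happens on/before the start of the maintenance period, then the participant will be summarized" in the selected regimen. For later switches, Section 6.4 says "Crossover participants who switched to the selected treatment regimen after the start of the maintenance dosing period will be summarized in a separate group".

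The Protocol gives a second route to weekly dosing. Table 5 can move a participant on any daily dose, in either group, to 20 mg weekly. The Table 4 footnotes carry the matching exceptions: for Group B, "unless a dose modification of a switch to a QW schedule is required for diarrhea/colitis management"; for Group A, "unless a dose modification of a switch to a QW schedule before Week 9 is required for diarrhea/colitis management".

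SAP Section 11.2 (Amendment 1) records that the maintenance duration and average-dose calculations were changed because the 2.5 mg daily regimen was selected. Neither document gives a separate rule for weekly dosing. The result is reported in Table 3.1.3 (SAP Appendix A).

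**The concern.** A first-to-last-dose denominator suits daily dosing, where each dose covers one day. A weekly dose covers seven. Over n weekly doses the formula counts the six non-dosing days after every dose except the last, so it divides n doses by n - 1 full intervals plus one day. The same regimen, taken perfectly, then yields a different mg/day value depending only on how long the participant stayed on it.

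The nominal maintenance rates are close: 20/7 = 2.857 mg/day in Group A and 2.5 mg/day in Group B, a gap of 0.357. Values that end on daily dosing are exact, while values that end on weekly dosing are pushed up, most for early stoppers. No statistical comparison of the groups is planned, but Table 3.1.3 shows both regimens on this measure, and a reader will set the columns side by side. SAP Section 5.1 lists "the number of observations, mean, standard deviation, median, minimum, and maximum" as summary statistics. The mean and maximum are more exposed to a few short-stay participants than the median is.

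**Working it through.** The documents state no mg/day figure, so there is none to reproduce. The check is direct arithmetic.

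**Inputs**
- Average = total mg / D, with D = last dose date - first maintenance dose date + 1 (SAP 6.4).
- Group A maintenance: 20 mg every 7 days (SAP 3 and 5.2).
- Treatment length about 52 weeks (Protocol synopsis, Estimated Duration of Participation), of which 8 weeks are initial daily dosing: 52 - 8 = 44 weekly doses.
- First 50 participants assigned 1:1: about 50 x 1/2 = 25 in Group A. The later 70 went to the selected regimen, which SAP 11.2 identifies as Group B.

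**Formula.** For n on-schedule weekly doses, D = 7(n - 1) + 1 = 7n - 6. Counting the full last interval gives D + 6 = 7n days, hence 20n/7n = 2.857 mg/day for every n. The SAP gives 20n/(7n - 6). The ratio is (D + 6)/D, so the excess is 6/D.

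| Weekly doses n | D (days) | SAP average, 20n/D (mg/day) | Excess over 2.857 |
|---|---|---|---|
| 44 | 302 | 2.914 | +2.0% |
| 18 | 120 | 3.000 | +5.0% |
| 8 | 50 | 3.200 | +12.0% |
| 4 | 22 | 3.636 | +27.3% |
| 2 | 8 | 5.000 | +75% |
| 1 | 1 | 20.0 | +600% (7-fold) |

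The excess passes 5% only when D is below 6/0.05 = 120 days (17 or fewer doses), and 10% only when D is below 6/0.10 = 60 days (9 or fewer doses).

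**Dose level does not matter.** Eight doses of 10 mg give 80/50 = 1.60 against 10/7 = 1.429 mg/day, again +12%.

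**Daily then weekly (illustration).** Take 60 days at 2.5 mg, a 14-day interruption, then 4 weekly 20 mg doses. D = 60 + 14 + 21 + 1 = 96 and the dose is 150 + 80 = 230 mg. The SAP gives 230/96 = 2.396; counting the last interval gives 230/102 = 2.255. The excess is 6/96 = 6.25%.

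**Weekly then daily.** Ten weekly 20 mg doses (70 days) followed by 100 days at 2.5 mg give (200 + 250)/170 = 2.647 mg/day. Every weekly interval is complete, so there is no error. A crossover participant who ends on daily dosing is not affected.

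**Upper bound.** If only k of the 6 remaining days should count, for example because death or data cutoff intervenes, the excess is k/D. At 4 doses and k = 3 it is 3/22 = 13.6%.

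**The case against.** The strongest reply is that this is a convention and not a mistake. Section 6.4 defines the quantity completely, no stated figure is wrong, and the value is too high only against a full-interval convention that the SAP does not adopt. That holds for duration of treatment, where first-to-last dose is acceptable and is not challenged here. It does not hold for a rate in mg/day. The formula already counts the dose-free days of every weekly interval but the last, and Protocol Section 1.4 presents that time off as part of the rationale for the weekly regimen.

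A second reply is that the sponsor revisited this formula. Amendment 1 did change it, and did so because the daily regimen was selected. This shows the choice was deliberate and fitted to daily dosing. It does not remove the effect, because Group A is still tabulated.

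Third, the 27% and 7-fold figures are chosen illustrations. This stands. The treatment length that the Protocol expects gives about 2%, or 0.057 mg/day.

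Fourth, Table 3.1.3 is a nonstandard table whose shell is in a separate document. A suitable footnote may already exist; the documents do not show it.

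Fifth, Section 5.2 describes Group B maintenance as the 2.5 mg daily period and does not say which column holds a Group B participant moved to weekly dosing. This also stands, so an effect on the Group B column is possible but not established.

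**Conclusion.** The point holds at low severity. When the last maintenance dose was weekly, the average reported daily dose is too high by up to 6/D: about 2% at 44 doses, more for shorter exposures. Those affected are Group A participants who reached weekly dosing and did not cross over (at most about 25, actual number not given) and possibly participants moved to weekly dosing under Protocol Table 5. The percentages by dose count assume exact 7-day spacing, no missed doses and a full final interval.

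A reader might infer three stronger things that the documents do not support:
- **That the Group A mean is overstated by 12% or 27%.** The documents give no distribution of weekly dose counts, so no group-level figure can be derived.
- **That crossovers distort the Group A column.** Early switchers are summarized in the selected regimen and later ones separately. Those ending on daily dosing have exact values.
- **That other results are affected.** Response rate, the futility rule and the sample-size probability do not use this quantity, and compliance (SAP 6.5) divides by prescribed dose.

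**What to change.** Keep duration of treatment as first-to-last dose. For average daily dose in the maintenance period only, when the last maintenance dose was on a weekly schedule, use (last dose date - first maintenance dose date + 7) as the denominator, truncated at the earliest of death, data cutoff and start of new anticancer therapy. Two limits are needed:
- **Imputed dates.** Do not apply the rule if the last-dose date was imputed in any way under SAP 4.1.4, which can use the discontinuation date, the month end or 31 December. For example, a true last dose on 3 June with the day missing and discontinuation on 10 July is imputed as 30 June. D is then already 27 days too long, and adding 6 would worsen it.
- **Initial period.** Do not extend the initial daily-dosing period in the same way. A weekly dose on Day 54 would carry it to Day 60, and with maintenance starting on Day 57 the days 57 to 60 would be counted twice.

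The SAP should also state which column holds participants moved to weekly dosing under Protocol Table 5.

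The cost is one derivation rule with three truncation events and one exception, plus a footnote. The downside is a denominator that differs from the reported duration.

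Minimum alternative, with no new derivation: keep the formula and footnote Table 3.1.3 that values ending on weekly dosing are computed over first-to-last-dose days and are too high by up to 6/D.
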